3.6 Risks and benefits

As of 12 July 2014, over 10,900 subjects were enrolled in studies with secukinumab, with over 8,600 having received active drug at doses ranging from single and/or multiple doses of 0.1 mg/kg to 30 mg/kg i.v. and 25 mg to 300 mg s.c.

In total, 4,546 patients with moderate to severe plaque psoriasis were included in studies in the registration program. These included 3,430 patients treated with secukinumab in 10 phase II/III studies, 2,727 of whom were treated for at least 6 months and 2,029 for at least 48 weeks. The Phase III program demonstrated secukinumab to be very effective in treating plaque psoriasis, with 300 mg being the dose that delivered the most clinically meaningful benefit to patients. The majority of patients treated with this dose achieved clear to almost clear skin, as shown by PASI 90 response and Investigator Global Assessment modified (IGA mod) 2011 0 or 1 response.

The 3,430 psoriasis patients treated with secukinumab covered 2725 patient-years of exposure during the 10 Phase II/III clinical trials. The overall exposure-adjusted incidence of AEs per 100 patient-years over the entire treatment period was lower in the 300 mg and 150 mg secukinumab groups (236.1 and 239.9, respectively) compared with the placebo and etanercept groups (351.8 and 243.4, respectively). Most AEs in all treatment groups were mild or moderate in severity.

Secukinumab obtained EMA approval in February 2015 for the treatment of moderate to severe plaque psoriasis in adults who are candidates for systemic therapy.

The Investigator's Brochure (IB) provides a more detailed review of the pre-clinical and clinical information on secukinumab.

4 Population

The study plans to enroll 406 adult men or women, of which 365 are evaluable patients, diagnosed with moderate to severe chronic plaque psoriasis for at least 6 months. The patients must be candidates for systemic therapy and may be treatment naïve or have failed to respond to other systemic therapy, including cyclosporine, methotrexate, psoralen combined with ultraviolet A (PUVA), or to an anti-TNF α (or is intolerant and/or has a contraindication to these). The study plans to involve about 50 centers.

The extension phase will include 306 of the patients taking part in the core study.

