A treatment-emergent adverse event is defined as any adverse event that develops after initiation of the study treatments or any event already present that worsens following exposure to the study treatment.

Non-treatment emergent adverse events will be listed separately.

Additionally, differences between cohorts in total number of AEs / SAEs/ AEs of special interest, by study period and overall, will be done with a poisson regression model adjusting over time of exposure, age at baseline (tertile), sex, number of comorbidities and BMI class.

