2.8.1.1 Adverse events of special interest / grouping of AEs

Neutropenia and candida infection will be considered as adverse events of special interest.

Adverse events of special interest will be summarized by cohort and overall divided by study phase on safety set and also will be listed separately. The below events from RMP will also be summarized, if possible. Differences between cohort will be assessed by means of a logistic model with factors (time of exposure, age at baseline (tertiles), gender, total number of comorbidities, BMI class). Tertiles will be calculated from SAS using PROC Univariate of age at baseline. If identifying the below SI is difficult, all RMP related events will be summarized.

Differences between cohorts on total number of events for each group of events (if possible) reported in the RMP will be analyzed by means of a Poisson regression model adjusting per time of exposure, age at baseline (tertile), gender, BMI class and total number of comorbidities according to the table below.

Event of special in	Comorbidities to	
Potential Risk	SMQ or SOC or HLT or PT (MedDRA Version 20.0)	take into account in the model
Infections and infestations	SOC: Infections and infestations	Diabetes (every form) (Y/N)
		Previous biologic and systemic therapy (yes vs no)
Neutropenia	PT: Agranulocytosis	

The total number of comorbidities for RMP related table will be defined by presence of at least one of the comorbidities mentioned below.

	Autoimmune neutropenia Band neutrophil count decreased Band neutrophil percentage decreased Febrile neutropenia Granulocyte count decreased Granulocytes maturation arrest Granulocytopenia Granulocytopenia neonatal Idiopathic neutropenia Leukopenia Metamyelocyte count decreased Myeloblast count decreased Myeloblast count decreased Neutropenia Neutropenia neonatal Neutropenic colitis Neutropenic colitis Neutropenic sepsis Neutrophil count decreased Neutrophil percentage decreased Pure white cell aplasia White blood cell count decreased	previous biologic therapy (yes vs no)
Malignant or unspecified tumours	SMQ: Malignant or unspecified tumours	SOC: "Neoplasms benign, malignant and unspecified"

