Section 2.2 Analysis sets

Analysis Sets added for clarity or additional analyses:

- All patients: all patients who signed informed consent and entered in the study, including screen failure.
- Core phase completers set: All patients who completed the Core phase visits (Week 24) are called core phase completer set.

Analysis Sets updated/ clarified (in bold):

- Safety: all enrolled patients **included in the FAS population** who were given at least one dose of study drug.
- Intent-to-treat (ITT): all patients included in the safety population with at least one post-baseline efficacy assessment and with the Cw6 assessment.

Section 2.3.1:

By visit disposition summary table is added.

Section 2.3.2:

P-values of comparison of cohorts will be analysed based on stratified CMH, and logistic model with covariates (for categorical variables) and ANCOVA (for continuous variables).

Total number of comorbidities (all medical histories) between cohorts will be analyzed by Poisson model adjusted by covariates.

Section 2.4.2:

Previous psoriasis therapies will be analysed by logistic model and total number of such therapies will be analysed by Poisson model after adjusting for covariates.

Section 2.5:

The model factors are clarified in the SAP.

Non-responder imputation is added. Analyses based on NRI for primary and secondary efficacy endpoints are added.

Modelling approaches of PASI scores and IGA scores have been included based on MMRM. Modelling of IGA0/1 responder is also added.

Section 2.8.1

The AEs comparison of cohorts will be done based on CI and pvalues generated from logistic model or poisson model (for total number of events overall).

The AESI of RMP related events will be summarized and compared based on logistic model approach.

Section 2.8.4

ANCOVA model for vital signs are added.

5 Appendix

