5.4.3 Secondary analysis

The SAS procedure PROC FREQ with Method= NEWCOMBE option, will be used to derive Confidence intervals for response rates with the following sample SAS code:

PROC FREQ DATA = \dots ;

BY visit;

TABLES trtan*resp / riskdiff (column=2 cl=(NEWCOMBE));

RUN;

The SAS procedure PROC MIXED will be used for linear mixed model for repeated measurements (MMRM) analysis with the following sample SAS code:

PROC MIXED DATA=dataset noclprint;

CLASS cohort vis1n usubjid MissingPattern;

MODEL Changes= cohort week0 dropout visit prop_score

cohort*visit cohort*MissingPattern;

REPEATED visit/subject=usubjid TYPE=cs;

LSMEANS cohort*visit/pdiff cl;

RUN;

The SAS procedure PROC PHREG, will be used to perform computed using a stratified Cox proportional hazards regression model with Cw6 group and baseline PASI as explanatory variable with the following sample SAS code:

PROC PHREG DATA=....;

CLASS trtpn baseline ..;

MODEL var*censor(0)= trtpn base.../rl ties=efron ;

RUN;

The SAS procedure PROC LIFETEST, will be used to perform log-rank test and to plot Kaplan-Meier estimates of the cumulative rate for each cohort with the following sample SAS code:

PROC LIFETEST DATA=... PLOT;

TIME timevar*censor(0);

STRATA ...;

RUN;

The SAS procedure PROC CORR, will be used to perform Spearman's (or Pearson's product moment correlation depending on data distribution) correlation with the following sample SAS code:

PROC CORR DATA = pearson/spearman OUTP=CORR;

VAR VAR1 VAR2;

RUN;

The SAS procedure PROC UNIVARIATE with NORMAL option, will be used to check the normality with the following sample SAS code:

PROC UNIVARIATE DATA = normal;

VAR var.../options...;

CLASS var;

RUN;

The SAS procedure PROC UNIVARIATE, will be used to perform Wilcoxon signed rank test with the following sample SAS code:

PROC UNIVARIATE DATA =;

VAR var...;

RUN;

The SAS procedure PROC TTEST, will be used to perform paired t-test with the following sample SAS code:

PROC TTEST;

PAIRED VARbefore*VARafter;

RUN;

The SAS procedure PROC FREQ with EXACT statement equal to MCNEM or AGREE will be used to perform Mc Nemar's test with the following sample SAS code:

PROC FREQ DATA =;

TABLES trtan*resp;

EXACT MCNEM or AGREE;

RUN;

SAS code for poisson regression model

proc genmod data=demo_ae ;

class cw6 sex age_group/ param = glm;

model numev = cw6 age_group sex / type3 dist=poisson;

lsmeans cw6 /ilink cl diff;

lsmeans age_group /ilink cl diff;

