lsmeans sex /ilink cl diff;

run;

proc genmod data=demo_ae ; class cw6 (param = ref ref = "NEGATIVE") sex (param = ref ref = "M") age_group (param = ref ref = "<=40 years"); model numev = cw6 age_group sex / type3 dist=poisson ; estimate "IRR Cw6 (POS vs NEG) " cw6 1 -1; estimate "IRR Age (>40 vs <=40)" age_group 1 -1; estimate "IRR Sex (Female vs Male)" sex 1 -1;

run;

PASI Changes vs baseline: Linear Mixed Model for Repeated Mesurements (MMRM):

The SAS procedure PROC MIXED will be used in the analysis, in particular:

proc mixed data=dataset noclprint;

class cohort vis1n usubjid MissingPattern;

model Changes= cohort week0 dropout visit prop_score

cohort*visit cohort*MissingPattern;

repeated visit/subject=usubjid type=un;

lsmeans cohort*visit/pdiff cl;

run;

where changes includes all changes vs week 0 of PASI; the dropout variable is the missing pattern (i.e. a categorical variable with values of 1, 2, 3 etc.. representing completers, 1 assessment missing, 2 assessments missing, 3 assessment missing etc. in considered dependent variable –e.g. PASI); the prop_score variable is the propensity score. In order to take all the confounding factors into account, the propensity score methodology will be applied and will be included in the final model, as described above. Propensity score will be derived using logistic regression model considering cohort as the dependent variable and baseline covariates as the factors in the model. The derived propensity score will be used as the covariate in the MMRM model.

MMRM with MI approach

Multiple imputation will be performed in SAS using the following three-stage approach:

PROC MI will be applied for each PASI change (or each post baseline PASI score) containing some missing values, which results in creation of multiple copies of this dataset. All copies contain identical values of the non-missing data items, but different values imputed for missing items. The following SAS statement will be used:

proc mi data=PASI_in out=PASI_out seed=1425;

var cohort Baseline PASI score PASI score at week 1 PASI score at week 2 PASI score at week 3 PASI score at week 4 PASI score at week 8 PASI score at week 12 PASI score at week 16 PASI score at week 20 PASI score at week 24;

class cohort;

monotone regression;

run;

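### Adverse-event counts are compared with plain Poisson regression and no allowance for overdispersion, so inference for total AEs is likely to be too optimistic; the printed code also leaves out the exposure adjustment that the text requires

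*SAP*

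**What the plan says.** SAP 2.8.1 adds a count analysis to the per-patient logistic comparison of AEs. For total AEs, SAEs and special-interest events, by study period and overall, the cohort comparison "will be done with a poisson regression model adjusting over time of exposure, age at baseline (tertile), sex, number of comorbidities and BMI class". SAP 2.8.1.1 plans a "Poisson regression model adjusting per time of exposure, age at baseline (tertile), gender, BMI class and total number of comorbidities" for event groups from the risk management plan. Both passages name exposure, but neither says whether it is a covariate or a log offset. Neither mentions a dispersion check, a scale parameter, robust variance or a negative binomial alternative.

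SAP 5.4.3 prints two Poisson fits, both with the same model: "model numev = cw6 age_group sex / type3 dist=poisson". There is no exposure term, offset, BMI class, comorbidity count or scale option. The second fit takes 40 years or younger as its age reference level, where the text asks for tertiles. Its cohort estimate carries the label "IRR Cw6 (POS vs NEG"), that is, an incidence rate ratio.

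The use is inferential. SAP Section 4 states: "The AEs comparison of cohorts will be done based on CI and pvalues generated from logistic model or poisson model". Comparing safety between cohorts is a secondary objective (Protocol 2.2, SAP Table 1.2-1).

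**The concern.** A Poisson model fixes the variance of each patient's count at its mean. AEs recur within patients, and some patients report more than others, so the variance usually exceeds the mean. Standard errors are then too small, and a difference between Cw6 cohorts in AE burden can look significant by chance too often. The SAP plans for other model failures (non-normality in 2.3.2, separation in 5.4.1, non-convergence of the unstructured covariance in 2.7.2) but not for this one.

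Exposure matters because follow-up is unequal and depends on response. Patients below PASI 50 stop treatment at week 16 (Protocol 5.5.9). Entry to the extension needs PASI 75 after 24 weeks (Protocol 4.3), and about 306 of 406 patients are expected to enter. The extension may end early by region (Protocol 5.5.12). If response differs by Cw6 status, which is the trial's question, time at risk differs too. A count model without exposure would then mix the two.

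**Working it through.** **Plan's own figures.** The documents give no power, precision or dispersion figure for the AE-count models. They supply only cohort sizes, which reproduce. With 80% response in both cohorts and a margin of 0.12, power for 219 + 146 is Φ(0.12/√[0.8·0.2·(1/219 + 1/146)] − 1.96) = Φ(2.808 − 1.960) = 80.2%. Dividing by 0.9 gives 365/0.9 → 406, and by cohort 244 and 163.

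**Inputs.**
- AE rate: 2.361 per patient-year. Protocol 3.6 gives the rates per 100 patient-years as "lower in the 300 mg and 150 mg secukinumab groups (236.1 and 239.9, respectively").
- Extension entry: 306/406 = 75.4%.
- Tests: two-sided (SAP 2.1). The 5% level is an assumption, as the SAP sets none for safety.
- Overdispersion k, with variance = μ + kμ²: an assumption, range 0 to 1. Read it as the variation left after the planned adjusters.

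**Formula.** Mean count: μ = 2.361 × 24/52 = 1.09 at 24 weeks and 2.361 × 72/52 = 3.27 at 72 weeks. The variance-to-mean ratio is φ = 1 + kμ. A nominal 5% Poisson Wald test has true size 2[1 − Φ(1.96/√φ)].

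**Simulation.** 2,000 trials per setting, 244 vs 163 patients, no true cohort effect, gamma-distributed patient rates, and age tertile and sex in every fit. Core phase: 90% followed for 24 weeks, the rest uniformly between 2 and 24. Overall: 75.4% followed for 72 weeks, the rest for 24. Monte Carlo error is about 0.5 points near 5%.

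| Period | k | φ | Size by formula | Poisson + offset | Poisson, no exposure (exposure handling as coded) | Offset + Pearson scale | Offset + robust SE |
|---|---|---|---|---|---|---|---|
| Core | 0 | 1.00 | 5.0% | 5.0% | 4.6% | 4.9% | 5.0% |
| Core | 0.25 | 1.27 | 8.2% | 8.1% | 8.1% | 5.6% | 5.8% |
| Core | 0.5 | 1.54 | 11.5% | 11.1% | 12.0% | 5.1% | 5.0% |
| Core | 1.0 | 2.09 | 17.5% | 17.4% | 17.8% | 5.4% | 5.4% |
| Overall | 0 | 1.00 | 5.0% | 3.9% | 8.0% | 4.2% | 4.6% |
| Overall | 0.25 | 1.82 | 14.6% | 13.4% | 17.2% | 5.5% | 5.2% |
| Overall | 0.5 | 2.63 | 22.7% | 21.2% | 24.2% | 6.0% | 5.5% |
| Overall | 1.0 | 4.27 | 34.3% | 33.4% | 35.3% | 5.6% | 5.0% |

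The overall formula values take every patient at 72 weeks, so they sit slightly above the simulated mixture. Entering exposure as a covariate gave the same sizes as the offset (overall 13.6%, 21.0%, 33.1%).

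**Leaving exposure out, equal extension entry, k = 0.** Mean follow-up is 60.2 weeks, μ = 2.73 and the squared coefficient of variation of follow-up is 0.118. So φ = 1 + 2.73 × 0.118 = 1.32 and the size is 8.8% (simulated 8.0%).

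**Leaving exposure out, unequal entry.** Assume 80% vs 70%. Mean follow-up is 0.8 × 72 + 0.2 × 24 = 62.4 weeks against 0.7 × 72 + 0.3 × 24 = 57.6 weeks. The false ratio is 62.4/57.6 = 1.083. Simulated with k = 0, the size is 27.6%, against 5.9% with the offset. With the split reversed, the false ratio is 57.6/62.4 = 0.92.

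**Rare events.** At an assumed 0.08 per patient-year, μ = 0.08 × 72/52 = 0.11. With k = 0.5, φ = 1.055 and the size is about 5.6%. Simulated sizes, with 80% vs 70% entry, were 5–6% in every fit.

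**The case against.** The best defence is that the text already requires exposure adjustment in both sections. The code matches none of the Poisson models described in the SAP, which suggests an unfinished template. This stands: a reader might infer that the sponsor plans to ignore exposure, or that the cohort with more extension entrants will appear to have more AEs. The documents show only that text and code disagree. The bias arises only if the code is run as printed, the 80% vs 70% split is illustrative, and Protocol 1.1 expects no difference between cohorts.

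A second defence is that the size of any overdispersion appears nowhere in the documents, and that BMI class and comorbidities may absorb part of it. This also stands. A reader might conclude that the intervals are certainly too narrow; the documents support only that this is likely.

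Third, a reader might infer that an offset is needed to control type I error. The calculations do not show that: covariate and offset performed alike, and the overall setting had only two exposure lengths, which a covariate fits exactly. The reason for the offset is interpretation.

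Fourth, the count models are additional. The logistic comparisons in 2.8.1 count each patient once, so repeated events do not distort them, and no decision rule rests on the Poisson p-values. This limits the consequence. It does not answer the absence of any dispersion handling in models whose p-values and intervals are to be reported.

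**Conclusion.** The concern holds for total AEs and common event groups. If k lies between 0.25 and 1.0, plain Poisson tests have a true size of about 8–17% in the core phase and 13–33% over the whole study, even with exposure handled properly. With k = 0 there is no inflation, and for rare SAE-like counts almost none, so the point should not be extended to SAEs. These sizes rest on the assumed k, a constant AE rate taken from the earlier programme and simplified follow-up.

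Separately, the SAP text and its only Poisson code conflict on exposure, BMI class, comorbidities and age grouping. Run as printed, the code would give a ratio of mean counts under a rate-ratio label. For the overall period that ratio would be biased, in either direction, whenever extension entry differs by cohort.

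**What to change.** 1. In SAP 2.8.1 and 2.8.1.1, specify Poisson regression with Pearson-scaled or robust standard errors, or negative binomial regression, for AE counts. The first two gave 4.2% to 6.7% in every setting simulated; negative binomial was not simulated.
2. State that exposure enters as an offset, the log of the time over which AEs are counted in each period. This is not always the duration of exposure in SAP 2.4.1: that runs from first to last dose, whereas 2.8.1 counts AEs to the last visit for patients who discontinue.
3. Rewrite the 5.4.3 code to match: offset, scale or robust option, age tertiles, sex, BMI class and comorbidities.

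The cost is a model option, a few words and wider intervals. On the log scale the widening is √φ: for k = 0.5, about 1.24 times at 24 weeks (√1.54) and 1.62 times at 72 weeks (√2.63). If there is no overdispersion, the results hardly change.

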2.8.1.1 Adverse events of special interest / grouping of AEs

Neutropenia and candida infection will be considered as adverse events of special interest.

Adverse events of special interest will be summarized by cohort and overall divided by study phase on safety set and also will be listed separately. The below events from RMP will also be summarized, if possible. Differences between cohort will be assessed by means of a logistic model with factors (time of exposure, age at baseline (tertiles), gender, total number of comorbidities, BMI class). Tertiles will be calculated from SAS using PROC Univariate of age at baseline. If identifying the below SI is difficult, all RMP related events will be summarized.

Differences between cohorts on total number of events for each group of events (if possible) reported in the RMP will be analyzed by means of a Poisson regression model adjusting per time of exposure, age at baseline (tertile), gender, BMI class and total number of comorbidities according to the table below.

Event of special in	Comorbidities to	
Potential Risk	SMQ or SOC or HLT or PT (MedDRA Version 20.0)	take into account in the model
Infections and infestations	SOC: Infections and infestations	Diabetes (every form) (Y/N)
		Previous biologic and systemic therapy (yes vs no)
Neutropenia	PT: Agranulocytosis	

The total number of comorbidities for RMP related table will be defined by presence of at least one of the comorbidities mentioned below.

	Autoimmune neutropenia Band neutrophil count decreased Band neutrophil percentage decreased Febrile neutropenia Granulocyte count decreased Granulocytes maturation arrest Granulocytopenia Granulocytopenia neonatal Idiopathic neutropenia Leukopenia Metamyelocyte count decreased Myeloblast count decreased Myeloblast count decreased Neutropenia Neutropenia neonatal Neutropenic colitis Neutropenic colitis Neutropenic sepsis Neutrophil count decreased Neutrophil percentage decreased Pure white cell aplasia White blood cell count decreased	previous biologic therapy (yes vs no)
Malignant or unspecified tumours	SMQ: Malignant or unspecified tumours	SOC: "Neoplasms benign, malignant and unspecified"
Major Adverse Cardiovascular Events (MACE)	Cardiac disorders (fatal outcomes only) SOC Vascular disorders (fatal outcomes only) SOC Brain injury (fatal outcomes only) PT Lateral medullary syndrome (fatal outcomes only) PT Post procedural stroke (fatal outcomes only) PT MACE (Myocardial infarction) [AIN457] Customized, company-specific search strategy Acute myocardial infarction PT Coronary artery embolism PT Coronary artery thrombosis PT Myocardial infarction PT Papillary muscle infarction PT Post procedural myocardial infarction PT Silent myocardial infarction PT MACE (Stroke) [AIN457] Customized, company-specific search strategy Basal ganglia haemorrhage PT Basal ganglia infarction PT Basal ganglia stroke PT Basal ganglia stroke PT Basilar artery thrombosis PT Brain injury PT	Diabetes (every form) (Yes/ No) Metabolic Syndrome (Y/N) Hypertension (Y/N) Elevated glucose (>=100mg/dL) (Y/ N) Waist circumference (>=120 man; >=88 woman) SOC: "Cardiac disorders"

	Brain stem haematoma PT Brain stem haemorrhage PT Brain stem infarction PT Brain stem stroke PT Brain stem thrombosis PT Carotid arterial embolus PT Carotid artery thrombosis PT Central nervous system haemorrhage PT Cerebellar antery thrombosis PT Cerebellar antery thrombosis PT Cerebellar haematoma PT Cerebellar haemorrhage PT Cerebellar infarction PT Cerebellar infarction PT Cerebral artery embolism PT Cerebral artery thrombosis PT Cerebral artery thrombosis PT Cerebral antery embolism PT Cerebral antery thrombosis PT Cerebral naemorrhage PT Cerebral haemorrhage PT Cerebral haemorrhage PT Cerebral infarction PT Cerebral infarction PT Cerebral infarction PT Cerebral infarction PT Cerebral venous thrombosis PT Cerebral venous thrombosis PT Cerebrovascular accident PT Embolic cerebral infarction PT Haemorrhage intracranial PT Haemorrhagic transformation stroke PT Intracranial haematoma PT Intracranial haematoma PT Intraventricular haemorrhage PT Ischaemic cerebral infarction PT Lateral medullary syndrome PT Moyamoya disease PT Post procedural stroke PT Putamen haemorrhage PT	"Endocrine disorders" "Gastrointestinal disorders" "Hepatobiliary disorders" PT: Transient ischaemic attack Carotid arteriosclerosis Cerebrovascular accident
	Cerebral venous thrombosis PT Cerebrovascular accident PT Embolic cerebral infarction PT Embolic stroke PT Haemorrhage intracranial PT Haemorrhagic cerebral infarction PT Haemorrhagic stroke PT Haemorrhagic transformation stroke PT Intracranial haematoma PT Intraventricular haemorrhage PT Ischaemic cerebral infarction PT Ischaemic stroke PT Lacunar infarction PT Lateral medullary syndrome PT Moyamoya disease PT Post procedural stroke PT Putamen haemorrhage PT Stroke in evolution PT Thalamic infarction PT	
	Vallenberg syndrome PT	
Immunogenicity		
Crohn's disease	PT "Crohn's disease"	"Gastrointestinal disorders"
Hepatitis B reactivation	HLT "Hepatitis viral infections"	-

SMQ= Standardized MedDRA Query

